cognitive behavioral relaxation techniques and found a 13.6% reduction in FIQR scores. From these studies, we estimate the difference between the yoga and structured exercise group is 17%. A between-group treatment difference of 14% reduction in symptoms represents a minimum clinically meaningful intervention effect.¹¹⁹ To be conservative, we will assume a 14% difference between treatment groups. The absolute score difference at 3 months is estimated to be approximately 7 points (6.79, 14% of 48.3). Assuming a common standard deviation of 17.6 and using a two-sample t-test, we will need 107 evaluable subjects in each arm to detect such a difference with >80% power and 5% Type I standard error rate.

We recognize the correlation of outcomes from subjects within the same yoga or exercise class may reduce the effective sample size compared to the same sample with independent observations. This possible “clustering effect” seen in group delivered interventions has implications for power. We have no preliminary data to estimate the intra-cluster correlation (ICC) for participants within the same group. However, based on similarly designed published studies, we expect the ICC to be relatively small and balanced across the two treatment arms since the cluster sizes will be similar.¹²⁰ Conservatively, we assume an ICC of 0.02 for both treatment groups. With 8 subjects per treatment group/class or cluster, the design effect is $1 + (8-1) \times 0.02 = 1.14$. Therefore, we will inflate our sample size by 14% to accommodate the potential clustering effects. We then need 122 evaluable subjects in each arm. With a conservative 20% attrition, we will then need $(122 \times 2) / 0.80 = 306$ subjects (153 in each arm).

D9b. Data analysis: Baseline characteristics of POYSE sample

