Since the primary outcome (FIQR total score) is measured repeatedly at baseline, 1, 3, 6, and 9 months, we will fit a repeated measurement analysis of covariance (ANCOVA) model with the four post baseline (1, 3, 6, and 9 months) FIQR total score as the response variables. The main predictors will be group (treatment arm), time (categorical), and their interaction. The model will be adjusted for baseline FIQR score. A random intercept will be used to adjust for the patient effect and to accommodate the correlation among the repeated measurements from the same patients. Another random intercept will be used to adjust for the potential clustering effect for patients in a specific yoga or exercise group. The primary analysis will evaluate the difference in FIQR score between the two treatment arms at 3-months (the primary end point) using appropriate contrast in this model. The sustained effect of intervention will be evaluated using appropriate contrast for the difference in FIQR change from 3-month to 6-month in this model.

D9d. Secondary analysis of primary outcome

For the FIQR total score, we will also define the patients with more than 30% reduction as “responders.” We will then compare the probability of responders between treatment arms using a generalized linear mixed model with a logit link. The responding status of each patient at **1, 3, 6, and 9 months** will be used as the outcome variables. Main predictors are group (treatment arm), time (1, 3, 6, and 9 months), and their interaction. A significant coefficient of group indicates a significant odds ratio of being a responder between the two arms at each time point. Each of the three domains of the FIQR score will be analyzed in the similar way to the total score.

D9e. Analysis of secondary outcomes

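### The FIQR model's patient random intercept assumes one variance and one correlation across months 1 to 9; if that fails, its standard errors risk being mis-sized, and no other structure is pre-specified

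*Combined protocol and SAP*

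**What the plan says.** Section D9c takes the four post-baseline FIQR total scores as responses. The fixed effects are arm, categorical time, their interaction and baseline FIQR. For dependence within a patient it gives a single term: "A random intercept will be used to adjust for the patient effect and to accommodate the correlation among the repeated measurements from the same patients". A second random intercept represents the yoga or exercise class. No residual covariance structure, random slope, visit-specific variance, robust standard error or fallback is named.

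The primary contrast is the arm difference at 3 months. The one sustained-effect contrast written out is the "difference in FIQR change from 3-month to 6-month in this model". D9c also lists sustained response 6 months after the intervention (month 9) and says that time points will be compared with one another, but it defines no contrast for either.

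Section D9e carries the same model to the Brief Pain Inventory and most other outcomes. The sensitivity analyses in D9f concern missing data only.

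**The concern.** A random intercept with independent residuals is compound symmetry: months 1 and 9 correlate as strongly as months 3 and 6, and every visit has the same variance. The class intercept is also constant over time, so it does not relax this.

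The visits are 2, 3 and 3 months apart. They run from the 12-week treatment period into six months without supervised sessions. Section B6 says that adherence falls and symptoms worsen once supervised exercise ends. A correlation that weakens with time, or a spread that changes, is therefore plausible, though the documents do not show it.

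The SE of a between-visit change depends directly on the correlation between those two visits. The SE at a single visit is built from a variance averaged over all four. If the assumed pattern is wrong, tests and intervals are too wide for some contrasts and too narrow for others, and nothing planned would reveal it. The protection under missing-at-random dropout claimed in D9f also relies on an adequately specified covariance. Leaving the structure open would also allow it to be chosen after the data are seen.

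**Working it through.** **1. The plan's own figure (D9a).** Inputs are a difference of 6.79, an SD of 17.6 and 5% type I error (taken as two-sided; the plan does not say), "with >80% power and 5% Type I standard error rate". The normal approximation gives n = 2 × (1.96 + 0.8416)² × 17.6² / 6.79² = 105.5, so 106; the exact t calculation gives 107, as stated: "Assuming a common standard deviation of 17.6 and using a two-sample t-test, we will need 107 evaluable subjects in each arm". Then 107 × 1.14 = 121.98, so 122 ("We then need 122 evaluable subjects in each arm"), and 244 / 0.80 = 305, against 306 stated (153 per arm). The figure is reproduced. It comes from a test at one time point, so no between-visit correlation enters it.

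**2. What the model estimates.** With complete data, a compound-symmetry fit recovers the average variance v and average covariance c of the true 4 × 4 covariance matrix. With n per arm:
- arm difference at visit j: model SE = √(2v/n), true SE = √(2σⱼ²/n);
- arm difference in change from j to k: model SE = √(4(v − c)/n), true SE = √(2(σⱼ² + σₖ² − 2σⱼₖ)/n).

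n cancels in the ratio of model to true SE. With equal SDs the change ratio is √((1 − ρ̄)/(1 − ρⱼₖ)), where ρ̄ is the mean of the six correlations. The actual type I error of a nominal 5% test is 2Φ(−1.96 × ratio). If compound symmetry is true, every ratio is 1.00.

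**3. Equal SDs, decaying correlation (assumed).** The documents give no between-visit correlations, so a range is used.

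| Correlation per month | ρ̄ | ρ(3,6) | ρ(3,9) | 3-to-6 ratio | 3-to-9 ratio |
|---|---|---|---|---|---|
| 0.85 | 0.507 | 0.614 | 0.377 | √(0.493/0.386) = 1.13 | √(0.493/0.623) = 0.89 |
| 0.93 | 0.729 | 0.804 | 0.647 | √(0.271/0.196) = 1.18 | √(0.271/0.353) = 0.88 |

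Type I error is 2.7% and 2.1% for the 3-to-6 change, and 8.1% and 8.6% for the 3-to-9 change. A 3-to-6 effect that would have 80% power with the correct SE has Φ(2.80 − 1.96 × 1.13) = 72%, down to Φ(2.80 − 1.96 × 1.176) = 69%. The ratio at every single visit, including month 3, is 1.00.

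In FIQR points, with SD 17.6, correlation 0.7 per 3 months and 122 per arm:

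| Contrast | True SE | Random-intercept SE |
|---|---|---|
| 3-month difference | 2.25 | 2.25 |
| 3-to-6 change | 1.75 | 2.01 |
| 3-to-9 change | 2.28 | 2.01 |

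A simulation at the same decay added a class ICC of 0.02 and 20% dropout (150 per arm, 250 runs). It gave ratios of 0.99, 1.09 and 0.88, each with Monte Carlo error of about 4-5%. The directions agree; the 3-to-6 ratio is smaller than the analytic 1.15, by less than two Monte Carlo errors.

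**4. Changing SDs (assumed 12, 14, 17, 18).** v = (144 + 196 + 289 + 324)/4 = 238.25, whose root is 15.44.

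| Arm difference at | Ratio | Type I error |
|---|---|---|
| 1 month | 15.44/12 = 1.29 | 1.2% |
| 3 months | 15.44/14 = 1.10 | 3.1% |
| 6 months | 15.44/17 = 0.91 | 7.5% |
| 9 months | 15.44/18 = 0.86 | 9.3% |

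With a constant correlation of 0.6, the change contrasts barely move here: 1.00 for 3-to-6 and 0.96 for 3-to-9.

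**The case against.** The strongest reply is that nothing confirmatory is shown to be wrong.

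- **The fault is conditional.** A reader might infer that the standard errors will be wrong. The documents do not support that: they report no SD by visit and no correlation between visits, and under compound symmetry nothing is lost. D9c also does not say that residuals are independent, so part of the fault is under-specification. This stands.
- **The primary analysis is largely insensitive.** A reader might infer that the 3-month result is compromised. With equal SDs it is untouched. The 10% figure needs SDs rising by half from month 1 to month 9, and the error is then conservative. The only SDs in the documents, 17.5 before and 17.6 after treatment in the cited yoga trial (D9a), do not suggest such a rise. They are raw SDs from another study, so they do not settle the question either. If SDs fell instead, from 1.15 to 0.85 of 17.6, the 3-month ratio would be 0.96 and the type I error 6.0%.
- **The defined sustained contrast errs on the safe side.** A reader might infer that the planned sustained-effect test has inflated false positives. Under decay, the specified 3-to-6 contrast loses power instead. The inflation falls on a 3-to-9 change that the plan never explicitly defines, although comparing time points is within its stated scope.
- **No single contrast is always worst hit.** Under decay it is the between-visit changes; under changing SDs it is the 1- and 9-month differences.

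These points limit the size and certainty of the concern. They do not supply the missing specification, and no planned sensitivity analysis varies the covariance.

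**Conclusion.** The point holds as a risk that the plan leaves open. As written, the model imposes compound symmetry on four unequally spaced visits during and after treatment, with no alternative or robust standard error.

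The sizes rest entirely on assumed covariances. Under equal SDs and decay of 0.85 to 0.93 per month, the specified sustained contrast loses power, a 3-to-9-month change would be tested at about 8 to 9% in place of 5%, and the primary SE is right. Under rising SDs, the primary SE is modestly too large and the later single-visit differences are tested at about 7.5% and 9.3%. Larger inflation for the 3-to-9 change (9.2-9.6%) appears only if decay and those rising SDs are assumed together. The sample size of 306 is unaffected. The consequence for the missing-at-random claim in D9f is one of principle; no size is put on it here.

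This is a cheap improvement that should be made, not a defect that invalidates the primary analysis.

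**What to change.** In D9c, keep the fixed effects and the class random intercept. Replace the patient random intercept with an unstructured within-patient covariance over months 1, 3, 6 and 9. Use Kenward-Roger degrees of freedom, and name a fallback in advance, such as heterogeneous Toeplitz, if the model does not converge. Apply the same wording to the D9e outcomes analysed in the same way. If a 9-month sustained effect is to be tested, write out its contrast.

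The cost is a change of wording. The model then has 4 × 5/2 = 10 within-patient covariance parameters in place of 2, easily estimated with about 244 evaluable patients. The fallback covers a possible convergence failure. Compound symmetry is a special case of the unstructured form, so little is lost if the present assumption is true.

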Medications are often the first line of therapy for fibromyalgia, but are frequently associated with adverse effects and show modest treatment benefits in clinical trials and practice.⁷ Aerobic exercise programs have proven benefit, but adherence to exercise is difficult to maintain and can lead to exercise-induced pain and myalgias if performed incorrectly. While the literature supports psychological treatments such as cognitive behavioral therapy (CBT) for reducing the overall symptoms of fibromyalgia, access to therapists with fibromyalgia expertise is limited. For relief, patients often turn to complementary and alternative medicine when traditional treatments are not effective.⁸ Yoga has shown initial promise for relief of fibromyalgia symptoms; presumably because yoga combines the benefits of exercise with relaxation and mindfulness practices. However, few yoga studies in fibromyalgia exist and those conducted have involved small sample sizes and yoga has not been compared to other treatments. With these challenges and limitations in mind, research to develop and compare different treatments for fibromyalgia, especially in veterans, is urgently needed.

We believe other treatment options are needed when pharmacological management fails to relieve fibromyalgia symptoms for veterans. Our long-term research objective is to develop, test, and implement novel treatments that address barriers to effective fibromyalgia treatment and that can be practicably applied in VA care settings. The **Pain Outcomes comparing Yoga versus Structured Exercise (POYSE)** Trial is a 2-arm parallel group, randomized clinical trial. The POYSE trial will target **306 veterans** with fibromyalgia and will compare the effectiveness of a yoga-based intervention (YOGA) with that of a structured exercise program (SEP). The trial will last 9-months and participants will undergo comprehensive outcome assessments at baseline, **1, 3, 6, and 9 months**.

Study Aims:

- 1) **To compare the interventions' (YOGA vs. SEP) effects on overall fibromyalgia severity at 1 month (early response), 3 months (immediate post-intervention) and at 6 and 9 months (sustained effects)**
- 2) **To compare the interventions' effects on specific fibromyalgia symptoms (pain, sleep, fatigue), functional impairment, and related outcomes (quality of life, depression, anxiety)**
- 3) **To compare the cost-effectiveness of the interventions**

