The intervention period will last for 3 months, after which time patients will be followed for an additional 6 months (total of 9 months). Treatment response will be assessed at **1, 3, 6, and 9 months after the date of the first intervention session**. The primary end point will be at 3 months (immediate post-intervention). Early response will be assessed at 1 month. Sustained response will be assessed at 6 and 9 months post-randomization. POYSE will last 4 years including 3 months for start-up; 2.5 years for recruitment; **9 months** for follow-up; and 6 months for data analysis and manuscripts.

Figure 2: POYSE Trial Design

D3. STUDY SITES

The RVAMC is an urban, university-affiliated, tertiary care center in Indianapolis which provides health care for more than 53,000 veterans. As Indiana's tertiary care facility, RVAMC receives referrals from VA facilities at Ft. Wayne and Marion, Indiana, and from nearby Danville, Illinois. The RVAMC provides acute inpatient medical, surgical, psychiatric, neurological, and rehabilitation care, as well as primary and specialty outpatient services. The clinics staff 75 primary care providers (faculty and resident physicians; advance practice nurses), caring for over 20,000 patients who make over 65,000 visits per year. The RVAMC is also the parent facility to three community based outpatient clinics—the Bloomington, Terre Haute, and Martinsville Outpatients Clinics. The Bloomington and Terre Haute CBOCs staff 4 primary care providers each and 1 provider is based at Martinsville. Each site provides primary care, prescription and other services to approximately 9,500 veterans in the Bloomington, Terre Haute, and Martinsville, IN metropolitan areas (all sites approximately 1 hour drive from Indianapolis).

D4. RECRUITMENT

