recruitment site (VAMC vs. CBOC). Within strata, randomization with block sizes of 4 or 6 will be executed to ensure balance. Once an eligible participant has been screened, has signed informed consent, and has completed the baseline measures the research assistant ([name]) or project coordinator ([name]) will submit a request to randomize the eligible participant. The randomization program locates the first unassigned record in the randomization list and assigns the participant to the group designated in that record. The participant identifier and date are written to the record. To ensure allocation concealment, only [name] and [name] will have access to the randomization table, but will not conduct outcome assessments. [name] will remain blinded to group assignment. No one will be allowed access to the folder of the randomization assignment until all baseline measures have been completed.

D7. POYSE INTERVENTION DETAILS

The POYSE interventions will last 3 months. The length of follow-up and schedule of outcome assessments at **1, 3, 6, and 9 months** after the date of the first intervention session are to detect **three** types of treatment effects: 1) **“early response” (at 1 month)**; 2) immediate post-intervention benefits at 3 months; and 3) sustained benefits at 6 and 9 months post-randomization (3 and 6 months post-intervention).

D7a. Overview of Yoga-based intervention

The yoga intervention (**Appendix 1**) will consist of three treatment components: 1) in-person group yoga sessions taught by a yoga therapist; 2) a relaxation audio recording for home-use; and 3) a DVD recording to reinforce concepts taught during in-person yoga sessions. The yoga intervention will complement standard medical treatments for fibromyalgia. It will involve 12 weekly group sessions of 8-12 patients per group. Each yoga session will last approximately 90 minutes and will be led by [name], Yoga Therapist (YT), who has over 30 years of experience in teaching yoga and meditation techniques to the general public and medical patients, including veterans. [name] has trained in several schools of yoga, but draws most significantly from the *Sivananda* tradition. She has also received veteran-specific yoga training in a program called “Warriors at Ease.” [name] will be the lead yoga therapist, but will train and supervise other yoga therapists to enhance future implementation.

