We will examine baseline characteristics (socio-demographic variables, medical and psychiatric comorbidity, duration of fibromyalgia, and current and prior pain treatments) of the POYSE sample. To evaluate the representativeness of study enrollees among all eligible patients, we will compare the enrollees and those who decline enrollment on their demographic characteristics. If there are systematic differences, these will be considered in the interpretation of the results of subsequent analyses. We will also examine differences in baseline characteristics between patients who remain in the study and those who dropout. Two-factor ANOVA models which include dropout status, treatment group (YOGA vs. SEP) and their interaction will be used for continuous variables. Logistic regression models with the same terms will be used for dichotomous variables.

D9c. Main analysis of the primary outcome (FIQR total score)

Our main analysis will employ a repeated measurement analysis of covariance (ANCOVA) model which is more powerful than two-sample t-test when the baseline outcome measurement is positively correlated with post baseline outcome.¹²¹ We plan an intent-to-treat analysis approach with the primary endpoint at 3 months and evaluation of “early” response at 1 month and “sustained” response at 3 and 6 months post-intervention. We will summarize this primary outcome at each time point (baseline, 1, 3, 6, and 9 months) for both arms. The difference between time points will be compared.

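### The sustained-effect contrast in D9c tests whether the arm difference changed between months 3 and 6, not the YOGA versus SEP difference at months 6 and 9 set out in Aim 1

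*Combined protocol and SAP*

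**What the plan says.** **Timing and meaning of the sustained effect.** Aim 1 (Section A) compares the two interventions on overall fibromyalgia severity at 1 month, then at "3 months (immediate post-intervention) and at 6 and 9 months (sustained effects". D2 says: "Sustained response will be assessed at 6 and 9 months post-randomization". D7 lists, among the treatment effects to be detected, "sustained benefits at 6 and 9 months post-randomization (3 and 6 months post-intervention". The opening of D9c plans to evaluate sustained "response at 3 and 6 months post-intervention", which D7 equates with study months 6 and 9.

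**The model.** D9c fits the FIQR total score at months 1, 3, 6 and 9, adjusted for baseline, with random intercepts for patient and class: "The main predictors will be group (treatment arm), time (categorical), and their interaction".

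**The contrasts.** For the primary question D9c names a difference in level: "The primary analysis will evaluate the difference in FIQR score between the two treatment arms at 3-months (the primary end point". For the sustained effect it switches to a difference in change: "The sustained effect of intervention will be evaluated using appropriate contrast for the difference in FIQR change from 3-month to 6-month in this model". No arm contrast at month 6 or month 9 is written out for the FIQR total score.

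**The concern.** The named contrast answers a different question from Aim 1. Aim 1 asks whether the arms differ at 6 and 9 months. The contrast asks whether the arm difference grew or shrank after month 3. A benefit that is perfectly kept gives an expected result of zero, as does the absence of any benefit throughout, and a significant result can mean that the benefit was lost.

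An analyst who follows the sentence would report as the sustained-effect result a test that is null in exactly the case the protocol hopes to show, and would have no instruction to report the arm difference at 6 or 9 months. A non-significant value could then be misread either as no sustained effect or as proof of maintenance. If the 6- and 9-month contrasts were added later, they would look like a post hoc choice. D9d and D9e model the FIQR domains and the Brief Pain Inventory in the same way as the total score, so the ambiguity may carry over to them.

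**Working it through.** **1. Notation.** Let D_t be the mean FIQR in SEP minus the mean FIQR in YOGA at study month t, so that a benefit of yoga is positive. Aim 1 asks for D6 and D9. D9c names D6 − D3.

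| Scenario | D3 | D6 | Level contrast D6 | Named contrast D6 − D3 |
|---|---|---|---|---|
| Never any benefit | 0 | 0 | 0 | 0 |
| Benefit fully kept | 6.79 | 6.79 | 6.79 | 0 |
| Half lost | 6.79 | 3.395 | 3.395 | −3.395 |
| All lost | 6.79 | 0 | 0 | −6.79 |

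The first two rows cannot be told apart by the named contrast. This is algebra and needs no assumption. D9 does not appear in it.

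**2. Inputs from D9a.** Effect: "The absolute score difference at 3 months is estimated to be approximately 7 points (6.79, 14% of 48.3"). SD 17.6, 5% error rate (taken as two-sided), ICC 0.02, 8 per class, 20% attrition. (14% of 48.3 is 6.76; the plan's own 6.79 is used here, and the difference is immaterial.)

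**3. Reproducing the plan's sample size.** A two-sample t-test with difference 6.79, SD 17.6 and 80% power needs 106.4, so 107 per arm. The design effect is 1 + 7 × 0.02 = 1.14; 107 × 1.14 = 121.98, so 122. Then 122 / 0.80 = 152.5, so 153 per arm and 306 in total. The plan's figures reproduce.

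**4. The named contrast.** Assumptions: 122 evaluable per arm also at month 6, equal SDs at both times, and a within-patient correlation ρ between months 3 and 6. The documents give no ρ; 0.5 to 0.8 is assumed. The class intercept in the planned model cancels in a change score, so no design effect is applied.

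SE = 17.6 × √(2(1 − ρ)) × √(2/122)

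Power = Φ(|δ|/SE − 1.96) + Φ(−|δ|/SE − 1.96)

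Example at ρ = 0.5: SE = 17.6 × 1 × 0.128 = 2.25. For total loss, 6.79/2.25 = 3.01 and power = Φ(1.05) = 0.854.

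| ρ | SE | 95% CI half-width (1.96 × SE) | Half-width as % of 6.79 | Rejects: fully kept, or no effect | Rejects: half lost | Rejects: all lost |
|---|---|---|---|---|---|---|
| 0.5 | 2.25 | 4.42 | 65% | 0.05 | 0.33 | 0.854 |
| 0.6 | 2.02 | 3.95 | 58% | 0.05 | 0.39 | 0.921 |
| 0.7 | 1.75 | 3.42 | 50% | 0.05 | 0.49 | 0.973 |
| 0.8 | 1.43 | 2.79 | 41% | 0.05 | 0.66 | 0.997 |

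If the observed change were exactly zero, the interval would therefore still include loss of 41% to 65% of the planned effect.

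**5. The direct month-6 contrast.** With the design effect and no gain from baseline adjustment, SE = 17.6 × √(2 × 1.14/122) = 2.41. Then 6.79/2.41 = 2.82, and power is about 0.81 if the benefit is fully kept. It rejects 29% of the time if half is lost and 5% if all is lost, which is the behaviour Aim 1 requires.

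**6. Sensitivity.** At ρ = 0.3 the half-width is 1.96 × 2.67 = 5.23 points (77% of 6.79), and total loss is detected 72% of the time. If the full 1.14 design effect is applied to change as well, detection of total loss is 81% to 99% for ρ 0.5 to 0.8, and 67% at ρ = 0.3. The 5% under full maintenance does not move in any of these.

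**The case against.** The best defence is that the change contrast is not read alone. The 3-month arm difference is tested in the same model, and the two together separate a kept benefit from no benefit. Whether a 3-month gain holds is also a fair everyday meaning of sustained. This stands as far as it goes: the contrast is a valid test of attenuation given a 3-month effect. It still does not give an estimate or interval for the arm difference at 6 or 9 months, and failure to reject is weak evidence that nothing was lost.

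Second, only Aim 1 states the between-arm comparison outright; D2, D7 and the opening of D9c mainly fix the timing. That is correct, but Aim 1 is the statement the analysis has to serve.

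Third, D9c promises summaries by arm at every visit, the model can estimate the later differences, and the D9d responder model covers months 6 and 9. However, summaries are not a named contrast, and a dichotomised responder outcome is not the FIQR total score.

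Fourth, the 3- and 6-month labels might be counted from the end of the intervention. The sentence just before uses 3 months in study time, so this is the less natural reading. It would give D9 − D6, which would bring in month 9 but would still be a change contrast.

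Finally, the power figures rest on an assumed correlation. The central point does not.

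**Conclusion.** The concern holds. The contrast named for the sustained effect does not estimate what Aim 1 calls the sustained effect, and on the natural reading it leaves out month 9. That conclusion follows from the definitions alone. The size is illustrative: with 122 evaluable per arm, SD 17.6 and ρ of 0.5 to 0.8, a fully sustained 6.79-point benefit gives a significant named contrast only 5% of the time, whereas the direct 6-month arm contrast detects it about 81% of the time. The 3-month primary contrast and the sample size are sound and are not affected. The plan should be corrected, but the correction concerns only the sustained-effect part of Aim 1.

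**What to change.** Replace the sustained-effect sentence in D9c with wording such as:

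> *The sustained effect will be evaluated by the between-arm difference in FIQR total score at 6 months and at 9 months, each as a contrast from this model with its 95% CI, secondary to the 3-month primary test. The between-arm differences in change from month 3 to month 6 and from month 3 to month 9 will be reported with 95% CIs as supplementary estimates of attenuation; a non-significant change will not be read as maintenance.*

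The cost is small: the same model and data, and no change in sample size. It adds two secondary comparisons and one further supplementary estimate (month 3 to month 9). The Bonferroni/FDR rule in D9e is written for secondary outcomes and does not clearly cover extra time points of the primary outcome, so the new contrasts should be labelled explicitly as secondary to the 3-month test. The change should be made before the later arm comparisons are examined.
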